PROTOCOL

Title: diEtitiaNs Helping pAtieNts CarE for Diabetes (ENHANCED)

IRB number: 798246

Protocol Version: 1

Version Date: 6/25/2016

PI: [name]

Staff on study: [name], [name], [name], [name], [name], [name]

1. Study Synopsis:

This will be a randomized-controlled trial to examine the impact of a Registered Dietitian (RD) led telemedicine program on diabetes outcomes for adults with type 2 diabetes. Two groups will be compared over one year; an intervention group who receives the telemedicine program versus a control group who receives usual diabetes care. Specifically, we will assess the 'D5,' which is a set of five treatment goals that when reached together, represent the gold standard for managing diabetes. D5 outcomes includes the proportion of participants in each group who achieve goal levels for blood glucose, blood pressure, tobacco use, statin use, and aspirin use.

2. Background:

Diabetes is a progressive, complex disease that requires frequent follow-up and ongoing care. Five key metrics—blood glucose, blood pressure, tobacco use, statin use, and aspirin use – commonly referred to as the “D5” are targeted in individuals with diabetes to reduce the risk of health complications¹. A recent review found that some risk factors were generally improving in U.S. adults with diabetes (e.g. blood glucose, LDL cholesterol), but 30-50% still did not meet individualized targets for glycemic control, blood pressure, or lipid control, and more than 20% remained smokers².

Poor diabetes control is also evident at local levels, particularly where access to diabetes care and education is more limited. In Hutchinson, MN, a rural region about 60 miles west of the Minneapolis metropolitan area, diabetes care quality is below the state average. The same is true for New Ulm Medical Center (NUMC). According to Minnesota Community Measurement, 30% of Hutchinson Health’s diabetes population is at goal on all D5 measures and 39% for NUMC. The breakdown of individual D5 measures for diabetes patients in Hutchinson and NUMC, respectively include:

- Blood pressure <140/90 mmHg (81%, 87%)
- Statin use (83%, 64%)
- Glycated hemoglobin (A1C) <8% (46%, 68%)
- Not using tobacco (86%, 88%)
- Taking daily aspirin as appropriate (99%, 99%)

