Most diabetes care in the U.S. is delivered by primary care providers (PCPs), although it is well documented that PCPs face significant time constraints to address all health issues adequately. The National Standards for Diabetes Self-Management Education³ emphasize the importance of a multidisciplinary clinical care team, which includes a registered dietitian (RD), to reduce disease risks. The role of the RD is well established for nutrition, physical activity, and behavior change education with high risk patients, but the involvement of RDs in other aspects of diabetes care is more limited, particularly as it relates to medication management. The few studies in this area have found encouraging results. Robinson and colleagues demonstrated that RDs who followed a lipid-titration algorithm were able to double the number of patients meeting lipid goals⁴.

Worth and Davies found that RDs who recommended, monitored, and titrated lipid-lowering therapies were able to achieve significant improvements in both total cholesterol and triglycerides⁵.

Innovative models are clearly needed to complement usual diabetes care. Achieving blood pressure, lipid, and glucose goals in adults with diabetes requires extensive lifestyle counseling, patient education, and pharmacological therapy, with frequent follow-ups to address challenges as they arise. This study will examine the impact of an RD-led, primary care integrated, telemedicine program on the D5 measures over one year as compared to a usual care group that will receive usual care only during this timeframe.

3. Specific Aims

The specific aims of this study are to:

1. Compare individual and composite D5 optimal care measures between patients in the intervention group vs. those in the usual care group.
2. Analyze changes in secondary outcomes including nutrition, physical activity, body mass index, medication adherence and gender.

Methods

4. Subjects and Setting:

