Measures. The primary outcomes will include changes in the D5 measures (A1C <8%, blood pressure <140/90 mmHg, not using tobacco, taking a statin and aspirin use as appropriate). These measures will be ascertained at baseline and 12 months after study enrollment. Interim D5 measures and those unavailable at follow-up will be extracted from Hutchinson Health and NUMC's EHR where possible. Secondary outcomes will include nutrition, physical activity, body mass index, medication adherence, confidence and satisfaction with diabetes management and gender. Specifically:

- Height
- Weight
- Waist Circumference
- Blood pressure
- Labs: A1c, fasting glucose, lipids
- Lifestyle questionnaire (see attachments)

Phone coaching

Phone visits will occur monthly over the course of one year, with some variability as needed such as more frequent phone contacts when a medication is started. They will be conducted by study coaches and last approximately 30 minutes. Topics will include:

- Brief lifestyle & medication assessment
- Nutrition coaching regarding appropriate choices (e.g. carbohydrate choices at meals/snacks, healthy fats, portion control).
- Physical activity recommendations
- If needed, medication initiation/titration for blood pressure, cholesterol or blood glucose

12-month/Final visit

The study follow-up visit will be similar to the baseline visit and occur at the Hutchinson Health clinic about 12 months later. The study follow-up visit will occur at NUMC for those patients identified from New Ulm. This will again be in-person and conducted by study coaches and lab personnel. The same measures will be taken as at baseline.

5. Study Procedures & intervention:

At the baseline visit, study participants will be randomized into the intervention or control group by computer using block randomization (block size 5).

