Coaches in this study will be registered dietitian/certified diabetes educators trained to address the D5 optimal care measures. They will also be trained in the use of a medication protocol that permits initiation and titration of blood glucose, lipid, and/or blood pressure medications (attachment). All coaching aside from the baseline and final visits is done via telephone and participants will generally receive a minimum of one call per month. The intervention is designed to complement to usual clinic-based primary care, with coaches documenting lab, biometrics, and medication adjustments in the EHR, along with documenting phone encounters and communicating directly with patients' PCPs as needed.

Documentation in the EHR uses an order created specifically for the study indicating the patient's research status; "opt-in" for those who choose to enroll.

To answer outcome evaluation questions, all individuals with a diabetes research study order will be extracted from the EHR along with baseline and 12 month D5 measures collected during respective visits. For comparisons between the intervention and usual care patients, the analysis

will examine mean changes in biometric risk factors and the percentage of patients meeting recommended levels for the D5 measures at baseline and after the one year intervention period. Medication changes will also be examined and compared between the two groups.

Study procedures will be approved in advance by the Allina Institutional Review Board.

Analysis

Analyses and power. A moderate effect size is expected of at least (Cohen's $w=0.25$) in this trial. Over one year, this translates into about 30% of the intervention group experiencing improvement in ≥ 1 D5 measure vs. 10% of usual care participants. Under the assumptions of 85% power, an alpha-level of 0.05, and a one degree of freedom test, 144 total participants (72 in each group) will be needed for this study. Mixed regression models will be used to compare D5 outcomes between the two study groups over time. Similar analyses will be conducted on secondary outcomes as well. An intent-to-treat framework will be used that will include all randomized participants.

6. Risk/ Safety information

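### The 0-3 entry rule makes about a third of eligible patients tobacco users, who can reach the five-goal D5 composite only by quitting, yet the planned model does not use baseline tobacco status

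*Combined protocol and SAP*

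**What the plan says.** - **Composite.** The Study Synopsis (Section 1) defines the D5 as "a set of five treatment goals that when reached together, represent the gold standard for managing diabetes". Aim 1 (Section 3) is to "Compare individual and composite D5 optimal care measures between patients in the intervention group vs. those in the usual care group".
- **Entry.** Section 4 admits patients who meet 0-3 of the five goals and excludes those who meet four or more.
- **Clinic rates (Section 2, Background; Hutchinson, then New Ulm (NUMC), in per cent).** Blood pressure 81, 87; statin 83, 64; A1C 46, 68; tobacco "Not using tobacco (86%, 88"; aspirin "Taking daily aspirin as appropriate (99%, 99". For all five together: "30% of Hutchinson Health’s diabetes population is at goal on all D5 measures and 39% for NUMC".
- **Intervention.** The call topics in Section 4 are a short lifestyle and medication review, nutrition, physical activity, and "If needed, medication initiation/titration for blood pressure, cholesterol or blood glucose". In Section 5 the medication protocol "permits initiation and titration of blood glucose, lipid, and/or blood pressure medications". The drug side effects listed in Section 6 belong to the same three classes. Section 5 also says that coaches are "trained to address the D5 optimal care measures".
- **Analysis.** Mixed regression models compare D5 outcomes between groups over time. No covariate or stratification factor is named. The sample size rests on 30% vs 10% improving in at least one D5 measure.
- **Measurement.** Tobacco (current, former, never) and aspirin (daily or every other day) are self-reported in the survey. The baseline survey is part of the visit that ends with randomization.

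**The concern.** A patient who uses tobacco at baseline fails the composite whatever happens to A1C, blood pressure and statin use, unless that patient quits. The entry rule concentrates such patients. If they form a third of each arm and few quit, the composite comparison carries a large block of near-certain failures in both arms. Leaving out a known predictor of that size costs precision, and a chance imbalance in tobacco use between two arms of 72 would go straight into the composite result.

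The model's baseline measurement does not make up for this. The entry rule leaves nobody at goal on all five by the eligibility data, so the baseline composite does not separate patients who have a realistic route to success from those who do not. Tobacco status does.

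Aspirin raises a smaller question: at clinic-wide attainment of 99%, a separately modelled aspirin outcome may rest on a handful of patients.

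**Working it through.** **1. The plan's own figure.** For 30% vs 10%, w = 0.20 / (2 × √(0.20 × 0.80)) = 0.25. With 144 patients, λ = 144 × 0.25² = 9, and a 1-df chi-square test at 0.05 has 85.1% power. The stated 144 and 85% reproduce, for improvement in at least one measure.

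**2. Tobacco users among those eligible, goals independent.** A tobacco user is eligible unless the other four goals are all met, so P(user and eligible) = P(user) × [1 − P(other four met)].
- Hutchinson: 0.14 × (1 − 0.81 × 0.83 × 0.46 × 0.99) = 0.14 × (1 − 0.3062) = 0.0971.
- NUMC: 0.12 × (1 − 0.87 × 0.64 × 0.68 × 0.99) = 0.12 × (1 − 0.3748) = 0.0750.

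P(eligible) = 1 − P(all five) − P(exactly four), with P(exactly four) = P(all five) × Σ(1 − p)/p.
- Hutchinson: 1 − 0.2633 − 0.4703 = 0.2664.
- NUMC: 1 − 0.3299 − 0.4384 = 0.2318.

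The shares are 0.0971/0.2664 = 36% and 0.0750/0.2318 = 32%, against 14% and 12% clinic-wide.

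**3. Allowing for correlation.** Independence gives composites of 26% and 33%, below the stated 30% and 39%, so the goals are positively correlated. A Gaussian model with one common correlation comes close to the stated values at 0.15 for Hutchinson (30.3%) and 0.20 for NUMC (38.8%). The tobacco shares are then 39% and 35%. Over 32-39%, that is about 47 to 56 of 144 patients.

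**4. What using tobacco status is worth (illustration).** Assumptions: the other goals are reached by 30% vs 10% regardless of tobacco use; a share q of users quits, equally in both arms; the user share is f. The composite rate is then 0.30 × (1 − f + fq) vs 0.10 × (1 − f + fq). Simulated power at 72 per arm (40,000 runs; chi-square test, and Cochran-Mantel-Haenszel test stratified by tobacco):

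| f | q | Composite rates | Unstratified | Stratified |
|---|---|---|---|---|
| 0.33 | 0.10 | 21.1% vs 7.0% | 70.3% | 72.6% |
| 0.33 | 0.05 | 20.6% vs 6.9% | 68.9% | 71.6% |
| 0.39 | 0.10 | 19.5% vs 6.5% | 65.5% | 68.3% |
| 0.39 | 0.05 | 18.9% vs 6.3% | 64.2% | 67.9% |

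The gain is about 2-3 points, 3.7 in the last row.

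**5. Aspirin.** By the same formula, P(off goal and eligible) is 0.01 × (1 − 0.81 × 0.83 × 0.46 × 0.86) = 0.0073 and 0.01 × (1 − 0.87 × 0.64 × 0.68 × 0.88) = 0.0067. Divided by P(eligible), this is 2.8% and 2.9%, or about 4 of 144. If two per arm were off goal and one arm corrected both while the other corrected neither, Fisher's exact p = 2 × C(72,2)/C(144,2) = 0.50. With four per arm, p = 2 × C(72,4)/C(144,4) = 0.12.

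**The case against.** Several stronger readings are tempting, and the documents do not support them.

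- **That the programme acts on only three goals.** A reader might infer this from the topic list and the drug classes. But coaches are said to be trained on the D5 as a set, the lifestyle and medication review is not itemised and could cover tobacco and aspirin, and the medication protocol is an attachment not in the text available. What can be said is that no specific tobacco or aspirin component is described.
- **That the trial is underpowered.** The powered quantity is improvement in at least one measure, and tobacco users are not blocked from that. The illustration moves 10% vs 30% onto a different outcome, so its 64-70% is not an estimate of this trial's power. Under independence, about 72% of eligible users miss exactly one of A1C, blood pressure and statin, while about 97% of eligible non-users miss two or three. One attainment rate for both groups is therefore a simplification, and the true dilution could be larger or smaller.
- **That a working programme would look null.** Aim 1 also compares the individual goals, and Section 5 adds mean biometric changes and medication changes. Effects on A1C, blood pressure or statin use could appear there.
- **That aspirin cannot show an effect.** The 99% is a clinic-wide figure for appropriate use; about 97% is implied among those eligible. The trial's self-reported item may give a different baseline.

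All four objections stand. None removes the case for using baseline tobacco status: the composite rate among users cannot exceed their quit rate, whatever the coaches do.

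**Conclusion.** The concern holds in a limited form. The entry rule raises the tobacco share from 12-14% to about 32-36% of those eligible under independence, and to roughly 35-39% with fitted correlation. The planned composite analysis leaves that predictor unused. The benefit of using it is modest, about 2-3 points of power in the illustration, but it comes free and guards against chance imbalance.

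This assumes that clinic-wide rates carry over to patients aged 40-75 who enrol, ignores the missing-measure rules, and takes the goals as independent or equally correlated. Tobacco use is a strong predictor as long as the quit rate is low compared with the composite rate among non-users. The quit rates of 5-10% are assumptions.

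On aspirin, the supportable statement is that there is probably little room to improve. Neither point affects the sample size of 144 or argues for replacing the D5.

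**What to change.** 1. In the Analysis paragraph, state that the D5 composite comparison will be stratified by, or adjusted for, baseline tobacco use (current vs not current). Stratification is the safer form. With 28 users per arm (39% of 72), 10% quitting and 30% reaching the other goals, fewer than one success is expected among users in the intervention arm (28 × 0.10 × 0.30 = 0.84). A logistic mixed model with a tobacco term could then fail to converge, whereas a Mantel-Haenszel analysis tolerates an empty stratum. Give a risk difference with its interval.
2. State that if few patients are off goal on aspirin, counts by arm with an exact interval will be reported rather than relying on the mixed model. Aspirin stays in the composite.
3. Reconcile the call topics in Section 4 with the training statement in Section 5, so that a reader can tell what the programme does about tobacco and aspirin.
4. Optional and supportive only: the proportion at goal on A1C, blood pressure and statin together, reported beside the D5.

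Item 1 uses data already collected before randomization and costs one sentence. Item 2 may mean no model-based test for aspirin alone. Item 4 adds one more outcome to interpret.

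### The continuous measures are to be compared as mean changes, with no stated use of the baseline value; a baseline-adjusted comparison would be more precise at almost no cost

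*Combined protocol and SAP*

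**What the plan says.** Section 5 (Study Procedures & intervention) describes the comparison of intervention and usual care patients: the analysis "will examine mean changes in biometric risk factors", alongside the percentages at D5 goal. The Analysis paragraph that follows adds "Mixed regression models will be used to compare D5 outcomes between the two study groups over time" and then "Similar analyses will be conducted on secondary outcomes as well". Section 3 words the second aim in the same way: "Analyze changes in secondary outcomes including nutrition, physical activity, body mass index, medication adherence and gender".

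The continuous measures are listed under Measures in section 4: height, weight, waist circumference, blood pressure and "Labs: A1c, fasting glucose, lipids", with body mass index among the secondary outcomes. On timing, Measures says of the D5 components "These measures will be ascertained at baseline and 12 months after study enrollment", and the paragraph on the final visit says "The same measures will be taken as at baseline". The Baseline study visit paragraph places randomisation at the end of that visit, after the survey, anthropometrics and blood draw.

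No fixed effects, covariates or constraint on the baseline means are given for any mixed model.

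**The concern.** A change score subtracts the whole baseline value, which fixes the baseline coefficient at 1. With equal variances at the two visits, the coefficient that minimises the error is r, which is below 1 for any measure that varies within a patient over a year. Fixing it at 1 costs precision and leaves the estimate correlated with any chance baseline difference: an arm that happens to start higher tends to fall further, and part of that fall is credited to treatment.

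Naming a mixed model does not by itself cure this, because its usual form for two visits returns the change-score estimate. A1c and blood pressure underlie two of the five D5 goals and are direct targets of the coaching and medication protocol. With 144 patients, avoidable standard error on these comparisons is worth removing.

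**Working it through.** **The plan's own figure.** With 30% and 10% improving in equal arms, the mean proportion is 0.20 and w = 0.20 / (2 × √(0.20 × 0.80)) = 0.25. Then N = (1.960 + 1.036)² / 0.25² = 143.65, rounded up to 144, with power 85.1%. The stated figure reproduces. It concerns a binary D5 improvement and does not depend on how continuous measures are analysed.

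**Inputs for the continuous measures.** From the documents: 72 per arm, equal allocation, one baseline and one 12-month visit. Assumed: the same SD at both visits (set to 1) and r between 0.3 and 0.9. The documents give neither an SD nor r.

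**Precision.** The variance per patient is 2(1 − r) for the change score and 1 − r² after linear adjustment for baseline. Their ratio is 2/(1 + r), so the change-score standard error is √(2/(1 + r)) times the adjusted one.

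| r | Change variance | Adjusted variance | SE ratio | Adjusted N matching 144 on change | Power on change when adjusted power is 80% |
|---|---|---|---|---|---|
| 0.3 | 1.40 | 0.91 | 1.24 | 94 | 62% |
| 0.5 | 1.00 | 0.75 | 1.15 | 108 | 68% |
| 0.7 | 0.60 | 0.51 | 1.08 | 122 | 73% |
| 0.9 | 0.20 | 0.19 | 1.03 | 137 | 78% |

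The fifth column is 144 × (1 + r)/2. The last is Φ(2.802/ratio − 1.960), where 2.802 = 1.960 + 0.842. At r = 0.5 the difference detectable with 80% power is 2.802 × √(2 × 1.00/72) = 0.47 SD on change scores and 2.802 × √(2 × 0.75/72) = 0.40 SD with adjustment.

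**Chance imbalance.** The baseline mean difference has SD √(2/72) = 0.167, so it exceeds 0.2 SD in either direction with probability 2 × (1 − Φ(1.2)) = 0.23. Given a baseline difference D, the change-score estimate is off by −(1 − r)D on average. With D = 0.2 SD, the size is 0.14 SD at r = 0.3, 0.10 at r = 0.5 and 0.02 at r = 0.9.

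**Simulation at r = 0.5, 72 per arm, complete data.** Over 20,000 trials the estimate's SD was 0.167 for the change score and 0.145 for ANCOVA. Correlation with the baseline difference was −0.50 and 0.00. In a second set of 150 trials, a mixed model with group, time and group-by-time terms reproduced the change-score estimate to rounding error. A mixed model with a common baseline mean had correlation 0.999 with ANCOVA, and both had SD 0.154, against 0.174 for the change score.

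**The case against.** The strongest reply is that the protocol is silent on adjustment and does not rule it out. A reader might infer that an unadjusted change-score analysis has been fixed. The text does not support that: the mixed models for secondary outcomes have no stated terms, and one with baseline as a covariate or with a common baseline mean would fit the wording. This stands. What remains is that mean change is the only contrast written down, and that the model is left open between forms with different standard errors.

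Second, the identity between the group-by-time model and the change score needs two visits and complete data. The protocol foresees measures unavailable at follow-up and extraction of interim D5 values from the EHR. This also stands. In a simulation at r = 0.5 with 20% of 12-month values missing at random (an assumed rate), the group-by-time estimate differed from the completers' change-score difference by 0.03 SD on average and by up to 0.11 SD. Its SD was nevertheless no smaller (0.180 against 0.176 over 60 runs), so the unconstrained model showed no recovery of precision.

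Third, a reader might infer bias from the remark on imbalance. Randomisation makes the change score unbiased on average. Imbalance is not left untouched but over-corrected, and the error is conditional on the baseline difference that happens to occur.

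Fourth, these are supporting measures. No effect size or power is claimed for them, so no stated power figure fails.

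**Conclusion.** The point holds as a free improvement. The stated contrast is less precise than a baseline-adjusted one at every r below 1, and nothing in the text commits the analyst to the better method. The change-score standard error is larger by 24%, 15%, 8% and 3% at r = 0.3, 0.5, 0.7 and 0.9. These sizes rest on equal variances, 72 per arm with complete follow-up, and a correlation that the documents do not supply. For a measure that tracks closely over a year, as weight may, the gain could be negligible.

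A reader might go further and conclude that the trial is underpowered or its main result compromised. The documents do not support that: the sample size rests on the binary D5 improvement, and the D5 comparison is not touched.

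**What to change.** In section 5, replace the statement on mean changes with wording such as:

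*Each continuous measure at 12 months (A1c, systolic and diastolic blood pressure, fasting glucose, lipids, weight/BMI, waist circumference) will be compared between arms by ANCOVA with its baseline-visit value as a covariate. The adjusted 12-month difference with its 95% confidence interval is the reported effect. Mean changes by arm will be given as description. Continuous secondary survey scores will be analysed in the same way.*

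The alternative is a mixed model with baseline as a response and a common baseline mean for both arms. It is nearly equivalent with complete data and also keeps participants whose 12-month value is missing, which suits the plan to include everyone randomised. One of the two should be named as the reported analysis.

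The cost is this wording and, for ANCOVA, one extra model parameter. No new data, visits or patients are needed.

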Sample. We will seek to recruit 144 participants for this trial. Patients will be recruited from Hutchinson Health in Hutchinson, MN and New Ulm Medical Center in New Ulm, MN in order to reach our recruitment goal. Hutchinson Health is an independent hospital/clinic that contracts with Allina Health to use their EHR. New Ulm Medical Center is part of the Allina Health system. Eligible patients will be identified by Allina Health informatics personnel based on the most recent available information contained in the EHR. Only EHR data from the previous 2 years will be considered to determine eligibility. Data will be extracted from the EHR system to identify individuals who are seemingly eligible for this study based on the criteria listed below. Each individual's most recent value for each measure from the previous 2 years will be considered. Values greater than 2 years old will be considered missing. Inclusion criteria will be:

- Diagnosis of type 2 diabetes
- Meeting 0-3 of the D5 measures
- Individuals meeting 0 of the D5 measures and have no more than two missing measures
- Individuals meeting 1 of the D5 measures and have no more than one missing measure

- Age 40-75 years
- 'Homed' in the Hutchinson Health clinic. This is defined as having at least one ambulatory care visit at the Hutchison Health clinic in the last 2 years.
- 'Homed' at the New Ulm Medical Center. This is defined as having at least one ambulatory care visit at NUMC in the last 2 years.

Exclusion criteria:

- Individuals meeting ≥ 4 D5 measures
- Individuals meeting ≥ 2 D5 measures with any missing measures
- Type 1 diabetes
- Chronic kidney disease (GFR <30)
- HIV
- Institutional residence
- Major cognitive or language barrier (as determined by program enrollment staff)
- Other active end-stage disease (e.g., late stage cancer or pulmonary disease)
- Actively receiving cancer treatment
- Pregnant

Study Recruitment

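### The 85% power and N=144 are computed for improvement in at least one D5 measure, an event not listed as an outcome, while the D5 comparisons are plural with no deciding endpoint or alpha rule

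*Combined protocol and SAP*

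**What the plan says.** The Analysis part of Section 5 (Analyses and power) assumes an effect of at least w=0.25 and gives it a concrete meaning: "this translates into about 30% of the intervention group experiencing improvement in ≥ 1 D5 measure vs. 10% of usual care participants". With 85% power, alpha 0.05 and a one-degree-of-freedom test, it concludes that "144 total participants (72 in each group) will be needed for this study".

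Elsewhere the outcomes are described differently:

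- Section 1 (Study Synopsis): "D5 outcomes includes the proportion of participants in each group who achieve goal levels", followed by the five measures. The same paragraph treats reaching all five goals together as the gold standard.
- Section 3 (Specific Aims), aim 1: "Compare individual and composite D5 optimal care measures between patients in the intervention group vs. those in the usual care group".
- Section 4, Measures: "The primary outcomes will include changes in the D5 measures", in the plural, with the five thresholds listed.
- Section 5, outcome evaluation: the analysis "will examine mean changes in biometric risk factors and the percentage of patients meeting recommended levels for the D5 measures".
- Section 5, Analysis: mixed regression models compare the groups over time on D5 outcomes, without saying which ones.

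Eligibility in Section 4 is restricted by "Meeting 0-3 of the D5 measures". The table of primary and secondary outcome measures lists component measurements and does not mark any of them as deciding the trial.

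**The concern.** The plan powers one event and announces others. A participant who improves on at least one measure is not the same as a participant who meets all five goals, or one who meets the A1C goal. The power paragraph is the only place where the responder appears, and it does not say whether improvement means newly reaching a goal or any favourable change.

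Two consequences follow. First, the stated 85% may be attached to comparisons for which it was never calculated, so a null result on the composite or on one measure could be read as the verdict of an adequately powered test. Second, with several primary comparisons and a single undivided alpha, a chance difference on one of them could be reported as a positive primary result. The plan does not say which comparison decides, so the choice could be made after the data are seen.

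**Working it through.** **1. The plan's own figure.** Inputs from Analyses and power: 30% and 10%, 1:1 allocation, alpha 0.05, 1 df, N=144.

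- Pooled rate = (0.30 + 0.10)/2 = 0.20.
- w = (0.30 − 0.10)/(2 × √(0.20 × 0.80)) = 0.20/0.80 = 0.25.
- Noncentrality = N × w² = 144 × 0.0625 = 9.0.
- Power from the noncentral chi-square with 1 df = 0.851. The smallest N reaching 0.85 is 144.

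The figure reproduces exactly. A 1-df chi-square test is two-sided.

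**2. Where the powered event appears.**

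| Place | What is compared |
|---|---|
| Section 1 | Proportions at goal on five measures |
| Section 3, aim 1 | Individual measures and the composite |
| Section 4, Measures | Changes in five measures (primary) |
| Section 5, outcome evaluation | Mean biometric changes; percentages at goal |
| Section 5, power | Improvement in at least one measure |

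Only the last row carries rates and a sample size. The responder could be derived from the changes in Section 4, but the plan does not say that it will be.

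**3. Does the 85% carry over to the composite?** Participants qualify with at most three measures met, so from the eligibility values they must gain at least 5 − 3 = 2 to meet all five (baseline-visit values may differ). If improvement means newly reaching a goal, everyone who goes on to meet all five is also a responder. The composite rates then cannot exceed the assumed 30% and 10%. The documents give no expected composite rates, so the following are assumptions, by the plan's own method at N=144:

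| Assumed composite rates | w | Power |
|---|---|---|
| 15% vs 5% | 0.167 | 52% |
| 20% vs 5% | 0.227 | 78% |
| 25% vs 5% | 0.280 | 92% |

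The spread shows that the power is not established. It does not show which value is right.

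**4. Family-wise error if five measures are each tested at 0.05 and any one suffices.**

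- Independent tests: 1 − 0.95⁵ = 0.226.
- Section 2 gives aspirin use as 99% at both clinics. With 99% in both arms and 72 per arm, exact enumeration of the Pearson test rejects about 0.6% of the time. Then 1 − 0.95⁴ × (1 − 0.006) = 0.190. At 95% in both arms the test rejects about 4.8% of the time and the figure returns to about 0.225.
- Correlated tests (equicorrelated normal test statistics, simulated; correlations assumed): about 0.21 at 0.3 and 0.18 at 0.5.

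**5. Cost of splitting alpha.** Bonferroni over five: alpha = 0.05/5 = 0.01. With N=144 and w=0.25 granted to every test, power = 0.664.

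Steps 1, 3 and 5 are two-proportion calculations. The planned mixed model may give somewhat different figures.

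**The case against.** The strongest reply is that the power paragraph first states w=0.25 as an expectation for the trial as a whole and uses the responder only as an illustration. N=144 gives 85% for any single 1-df test with that effect. This stands: a reader might infer that the sample size is valid for the responder alone, and that goes too far. What remains is that the plan links w=0.25 to just one event and gives no reason to expect it for the composite or for each measure.

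A second reply is that the responder is plain enough: anyone who gains a measure counts, whatever else is lost. That is a fair reading, and the documents give no basis for supposing that losses would be set against gains, or for putting figures on such a rule. The real ambiguity is whether improvement means reaching a goal.

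A third reply is that nothing in the plan says a single significant measure would make the trial positive. That is correct, so the error rates above are conditional. A reader might also count the composite as a sixth independent test and arrive at a higher figure. It cannot be independent, because it is determined by the other five.

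Attrition is a separate matter. The plan states no dropout allowance, but Section 4 says "Interim D5 measures and those unavailable at follow-up will be extracted from Hutchinson Health" and the New Ulm record where possible, and any residual loss would be an assumption.

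**Conclusion.** The concern holds in this form: the power statement belongs to one event that is not listed as an outcome and not fully defined, and the plan names no deciding comparison, testing order or multiplicity rule for the D5 comparisons it does state.

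The size depends on how the plan would be applied. Testing five measures at 0.05 with any one sufficing gives up to about 19-23% family-wise error under independence, the lower end if aspirin use among participants stays near the 99% clinic rate, and less if the tests are correlated. Controlling that error by Bonferroni leaves about 66% power, on the generous assumption of w=0.25 throughout.

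A reader might infer that 144 is the wrong number or that the composite is underpowered. The documents support neither. The calculation is correct for its stated inputs, and without expected composite rates the composite's power could be lower or higher than 85%.

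**What to change.** 1. Name one primary endpoint and the test for it at two-sided 0.05. Either choose the responder with at least one improved measure and define improvement, which keeps N=144 and 85% under the plan's own assumptions; or choose the all-five composite, state its expected rates, and restate the power that 144 participants give.
2. Make the remaining individual and composite D5 comparisons secondary, either adjusted for multiplicity or labelled non-confirmatory.
3. State that the 85% was computed for the responder with all 144 evaluable and is not established for the other D5 comparisons.

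The cost is wording and a revised power paragraph. Choosing the responder needs no extra participants or data. The downside is that the other D5 measures lose primary status. If the composite is chosen, the stated power may be less favourable.
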